8.3.5 Severity of Adverse Event or Suspected Adverse Drug Reaction

AEs including suspected ADRs will be classified according to severity, depending on the intensity of the event, as follows:

Mild: an AE which is well tolerated by the subject, causing minimum degree of malaise and without affecting activities of daily living (ADL).

Moderate: an AE that interferes with ADL.

Severe: an AE that prevents ADL.

Severity gradation of AEs including suspected ADRs must be distinguished from their seriousness gradation, which is defined according to event consequence. For example, headache can be mild, moderate, or severe but not necessarily serious in all these cases. See [Section 8.3.7](#) for Seriousness of AEs.

The investigator will be responsible for assessing the severity of AEs including suspected ADRs during the clinical study.

8.3.6 Expectedness of Adverse Event or Suspected Adverse Drug Reaction

An AE or suspected ADR is considered “unexpected” if the nature, seriousness, severity or outcome of the reaction(s) is not consistent with the reference information. The expectedness shall be determined by the Sponsor according to the reference document (ie, IB or Summary of Product Characteristics/Package Insert)for any serious ADRs (potentially related SAEs) for expedited safety reporting purposes.

8.3.7 Seriousness of Adverse Event or Suspected Adverse Drug Reaction

Adverse Events including suspected ADRs are considered “serious” if, in the view of either the investigator or Sponsor, they result in any of the following outcomes:

GRIFOLS
 
Bioscience Industrial Group
	Number IG1407 - Effects of Plasma Exchange with Human Serum Albumin 5% (PE-A 5%) on Short-term Survival in Subjects with "Acute-On-Chronic Liver Failure" (ACLF) at High Risk of Hospital Mortality	BIG-CL-PRT-000002	Version 6.0	Status	Retired	Effective Date	29-Mar-2023
						Page	70 of 102

- Death
- Life-threatening AE (life-threatening in the definition of “serious” refers to an event in which the subject was at risk of death at the time of the event; it does not refer to an event which hypothetically might have caused death if it were more severe)
- In-patient hospitalization or prolongation of existing hospitalization*
- A persistent or significant incapacity or substantial disruption of the ability to conduct normal life functions
- A congenital anomaly/birth defect
- An important medical event (important medical event in the definition of “serious” refers to those events which may not be immediately life-threatening, or result in death, or hospitalization, but from medical and scientific judgment may jeopardize the subject or/and may require medical or surgical intervention to prevent one of the other outcomes listed above)

* After the initial ACLF hospital discharge, hospitalization is to be considered only for hospital stay equal to or more than 24 hours. The following hospitalizations should not be reported as SAEs:

- Hospitalization or prolongation of hospitalization as part of a routine procedure followed by the center or clinical practice (according to the investigator’s criteria) for the treatment of ACLF
- Hospitalization for a survey visit, annual physicals, or social reasons
- Elective or pre-planned hospitalizations for a pre-existing condition that had not worsened from Baseline (eg, elective or scheduled surgery arranged prior to start of the study)
- Admissions not associated with an AE (eg, social hospitalization for purposes of respite care)

This definition permits either the Sponsor or the investigator to decide whether an event is “serious”. If either the Sponsor or the investigator believes that the event is serious, the event must be considered “serious” and evaluated by the Sponsor for expedited reporting.

8.3.8 Adverse Event Documentation

All AEs and SAEs occurring after the subject has **signed the ICF through the Final Visit (ie, end of study [Day 90 visit] or Early Discontinuation Visit)** must be fully recorded in the subject’s eCRF and SAE form (if serious) as well as in the medical record. If no AE has occurred during the study period, this should also be indicated in the eCRF.

It is the responsibility of the investigator to ensure that AEs are appropriately recorded.

At each visit, AEs will be elicited by asking the individual a non-leading question such as “Do you feel different in any way since the last visit?” Moreover, AEs will also be collected

GRIFOLS	Number						BIG-CL-PRT-000002		Version		6.0		Status		Retired		Effective Date		29-Mar-2023		
	IG1407 - Effects of Plasma Exchange with Human Serum Albumin 5% (PE-A 5%) on Short-term Survival in Subjects with "Acute-On-Chronic Liver Failure" (ACLF) at High Risk of Hospital Mortality																				
																			Page		71 of 102
Bioscience Industrial Group																					

through directly observed events or spontaneously volunteered by the subject. Clearly related signs, symptoms, and abnormal diagnostic procedures should preferably be grouped together and recorded as a single diagnosis or syndrome wherever possible.

The following variables must be recorded in the AE eCRF:

- The verbatim term (a diagnosis is preferred)
- Date/time of onset
- Date/time of resolution
- Severity (mild, moderate, severe)
- Causality (unrelated/not related, possibly related, definitely related)*
- Seriousness (yes, no)
- Action taken (with regard to IP)
- Other action (to treat the event)
- Outcome and sequel (follow-up on AE)

* An AE occurring before subject’s exposure to treatment will be labeled as “unrelated/not related”.

If it is a pre-existing AE that gets worse regarding intensity or frequency, it should be indicated.

For AEs that occur during a PE-A 5% session, the time of onset of the AE and the time of AE change materially in intensity and/or resolve will be captured in the eCRF.

In addition to the investigator’s own description of the AEs, each AE will be encoded according to the Medical Dictionary for Regulatory Activities (MedDRA).

For example, a laboratory test abnormality considered clinically significant, eg, causing the subject to withdraw from the study, requiring treatment or causing apparent clinical manifestations, or judged clinically significant in the context of the subject’s medical history by the investigator, should be reported as an AE. Each event must be described in detail along with start and stop dates, severity, relationship to treatment, action taken and outcome. Each event must be adequately supported by documentation as it appears in the subject’s medical or case file.

8.3.9 Event of Special Interest (if applicable)

There are no events of special interest related to Albutein 5%.

8.3.10 Disease Progression

In this clinical study, disease progression is defined as the worsening of a subject’s condition attributable to the disease for which the investigational product is being studied. It may be an

GRIFOLS
 
Bioscience Industrial Group
	Number	BIG-CL-PRT-000002	Version	6.0	Status	Retired	Effective Date	29-Mar-2023
	IG1407 - Effects of Plasma Exchange with Human Serum Albumin 5% (PE-A 5%) on Short-term Survival in Subjects with "Acute-On-Chronic Liver Failure" (ACLF) at High Risk of Hospital Mortality							Page
								72 of 102

increase in the severity of the targeted disease and/or increases in the symptoms of the targeted disease. Anticipated disease progression of ACLF includes, but not limited to: HE, gastrointestinal (GI) bleeding, portal hypertension, ascites, spontaneous bacterial peritonitis, HRS, and associated organ/system failure(s) (eg, liver, kidney, brain, coagulation, circulation and/or lung), which may develop at any time during the course of the disease.

The development of sequelae of ACLF and associated organ/system failure(s) during the clinical study should be considered as disease progression and not an AE, unless there is evidence suggesting a causal relationship between the study drug and the AE. Manifestations of sequelae of ACLF and associated organ/system failure(s) will be treated as disease progression and will be documented in the eCRF and subject’s medical records, but not immediately reported to the sponsor.

Hospitalization or prolonged hospitalization due to disease progression and/or the signs and symptoms of disease progression should not be reported as an SAE during the study.

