8.3.1 Warnings/Precautions

For complete information on Albutein 5% refer to the IB.

Plasma Exchange is a safe technique that may induce very well-known and therefore preventable and controllable AEs, according to the guidelines provided below. Considering the special vulnerability of the subjects studied, a number of precautions (in addition to the habitual measures) will be taken to minimize the risks of the procedure:

- PE will be carried out by specialized certified personnel, under direct and continuous supervision by the specialized physicians (intensivists, hepatologists, and hematologists).
- Vital signs and laboratory test parameters will be monitored more frequently than usual.

There are AEs that may be expected during the replacement procedure, due to the process of apheresis, the replacement fluid used, or as a result of the subject disease or idiosyncrasy. These AEs include, but not limited to, hypocalcaemia (manifesting as paresthesias, headache, vision alterations, nausea, cramps and chest oppression), anaemia and coagulation disorders secondary to coagulation factor dilution (mainly hypofibrinogenemia, with possible minor bleeding associated to severe thrombocytopenia), hypotension (accompanied by paleness, perspiration, bradycardia, nausea, vomiting, syncope, sphincter relaxation and seizures) (though the risk is minimal, since the infusion amount is equivalent to the extracted amount), allergic reactions with urticaria, dyspnea, wheezing, hypotension, tachycardia, facial reddening and palpebral edema, and AEs related to vascular access. Other events may be of psychological origin or may be inherent to the process, such as anxiety, headache, nausea, immunoglobulin level decreased, anemia, or pain after remaining immobile for several hours. However, these AEs will still be required to be reported.

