8.3.3 Adverse Event Definitions

8.3.3.1 Adverse Events

An AE is defined as any untoward medical occurrence in a subject or clinical investigation subject administered a medicinal product or study treatment and which does not necessarily have a causal relationship with this administration. An AE can therefore be any unfavorable and unintended sign (including any abnormal laboratory finding, for example), symptom, or disease temporally associated with the use of a medicinal product, whether or not considered related to the medicinal product. This includes worsening of a pre-existing condition or increase in frequency of a pre-existing condition.

An AE is also defined as any occurrence that is new in onset, expected, or aggravated in severity or frequency from the baseline condition, or abnormal results or diagnostic procedures including laboratory test abnormalities.

In this clinical study, deterioration of the targeted disease and symptoms associated with the targeted disease will not be considered an AE as long as the deterioration is anticipated and there is no evidence suggesting a causal relationship between the study drug and the AE. Anticipated disease progression includes, but not limited to HE, gastrointestinal (GI) bleeding, portal hypertension, ascites, spontaneous bacterial peritonitis, HRS, and associated organ/system failure(s) (eg, liver, kidney, brain, coagulation, circulation, and/or lung) (see [Section 8.3.10](#)).

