9.3.9 New Infections at End of Hospitalization

The number of subjects with new infections by the end of hospitalization is defined as the number (and percentage) of subjects with one or more AE categorized as an infection, or any and disease related

complication i.e. spontaneous bacterial peritonitis or an infection captured as “other” and described as an infection on the disease related complications CRF page, with a start date on or after the randomization date and before the end of hospitalization i.e. hospital discharge date. The percentage is calculated for each treatment group for all subjects in the ITT population. The percentage of subjects with new infections at end of hospitalization will be compared between treatment groups using the Fisher’s Exact or Chi-square test.

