10.2 Incidence of Disease-Related Complications

All disease-related complications are collected through day 90 and will be listed.

The number and percentage of subjects with at least one occurrence of each of the following disease-related complications after Day 1 will be presented by treatment and by visit, Anticipated disease progression includes, but not limited to:

- HE – including HE I, HE II, HE III, and HE IV
- Gastrointestinal (GI) Bleeding – including lower GI bleeding and upper GI bleeding
- Portal Hypertension
- Ascites
- Spontaneous Bacterial Peritonitis (SBP)
- Hepatorenal syndrome (HRS) – including Type 1 and Type 2
- Associated organ/system failure(s) – to be defined and summarized as described in [9.3.8](#)

In addition, the number of each type of disease-related complication will be counted for each subject and presented by treatment as a continuous variable and as a categorical variable with categories 0, 1, 2, 3, 4 or more. No analysis of treatment differences will be performed. Each type of HE, Gastrointestinal (GI) Bleeding, Hepatorenal syndrome(HRS) and associated organ/system failures will be counted separately.

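### GI bleeding, HRS and HE are split between the AE and complications records by a causality judgement that only the PE-A 5% arm can meet, and no planned table adds the two together

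*Protocol*

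**What the plan says.** Two protocol sections set the recording rule. Section 8.3.3.1 excludes deterioration of the target disease from the AE definition "as long as the deterioration is anticipated and there is no evidence suggesting a causal relationship between the study drug and the AE". It then gives examples: "Anticipated disease progression includes, but not limited to HE, gastrointestinal (GI) bleeding, portal hypertension", followed by ascites, SBP, HRS and organ failures. Section 8.3.10 repeats that such sequelae "should be considered as disease progression and not an AE, unless there is evidence suggesting a causal relationship between the study drug" and the event. Under 8.3.4, a rating of possibly related is enough to show such a link.

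The study drug is Albutein 5% given by plasma exchange (Protocol 2.1). Control subjects receive SMT (4.4.1.3), and there is no blinding (4.3.3). Section 8.3.1 lists "coagulation disorders secondary to coagulation factor dilution", with possible minor bleeding, among the events to be expected with exchange.

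SAP 10.1 tabulates AEs, including those within 72 hours of an exchange. SAP 10.2 tabulates, by arm and visit, "The number and percentage of subjects with at least one occurrence of each of the following disease-related complications after Day 1", and for the counts per subject it adds: "No analysis of treatment differences will be performed". For infections the SAP draws on both records: Section 9.3.9 counts "subjects with one or more AE categorized as an infection, or any and disease related" complication that is an infection, and 9.3.10 does the same for the infection rate. No such step is planned for bleeding, HRS or HE.

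**The concern.** Which record an event enters depends on a judgement made with the arm known, and in one arm the answer that leads to the AE record is not available. An SMT-arm GI bleed that is anticipated disease progression goes to the complications record. The same bleed in the PE-A 5% arm moves to the AE record once it is thought possibly related. Neither table then counts like with like.

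Bleeding is where this matters most, because the protocol itself expects a coagulation effect of the procedure. Protocol 9.1.3 bases safety comparisons on a review of descriptive tables, so a table that is skewed by its inputs feeds straight into the conclusion.

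**Working it through.** The plan states no figure on this point. The check is a comparison of the sections, followed by an illustration of size.

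**1. Can the exception apply in both arms?** It needs evidence of a link to the study drug (8.3.3.1, 8.3.10). SMT subjects do not receive it, so the share of SMT events that are attributed is 0. In the PE-A 5% arm it is some f between 0 and 1.

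**2. Size of the distortion.** Let r be the true risk of GI bleeding, equal in both arms. The documents give neither r nor f. I assume r = 10-30% and f = 10-50%, and that an attributed event appears only as an AE.

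- AE table: r × f (PE-A 5%) versus 0 (SMT)
- Complications table: r × (1 − f) versus r, a risk ratio of 1 − f
- Both sources pooled: r versus r, a risk ratio of 1.00 for every f

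| r | f | AE table, PE-A vs SMT | Complications table, PE-A vs SMT | Complications risk ratio |
|---|---|---|---|---|
| any | 0% | 0% vs 0% | r vs r | 1.00 |
| 10% | 10% | 1.0% vs 0% | 9.0% vs 10.0% | 0.90 |
| 10% | 50% | 5.0% vs 0% | 5.0% vs 10.0% | 0.50 |
| 15% | 25% | 3.75% vs 0% | 11.25% vs 15.0% | 0.75 |
| 30% | 10% | 3.0% vs 0% | 27.0% vs 30.0% | 0.90 |
| 30% | 50% | 15.0% vs 0% | 15.0% vs 30.0% | 0.50 |

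A real excess can also vanish from the complications table. With a true 20% on PE-A 5% against 15% on SMT and f = 25%, it shows 20% × 0.75 = 15% against 15%. With 20% against 10%, f = 50% has the same effect.

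**3. The Day 1 window.** For safety endpoints, SAP 6.1.2 sets Day 1 as the date of the first exchange (PE-A 5%) or of randomization (SMT). SAP 6.1.6 counts TEAEs from the first exchange. SAP 10.2 counts complications after Day 1. Read literally, a GI bleed on the day of the first exchange that is judged unrelated is not an AE, so it is not in 10.1. It is not after Day 1, so it is not in the 10.2 summary either. It would appear only in the complications listing. The SMT arm also loses its Day 1, but that day contains no exchange.

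**4. Precision of a pooled comparison.** At r = 15% and the planned 190 per arm, the 95% CI half-width is 1.96 × √(2 × 0.15 × 0.85 / 190) = 7.2 points. SAP Section 2 says the study stopped early and the documents do not give the final number, so with fewer subjects the interval would be wider.

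**The case against.** The strongest reply is that separate recording is inferred. SAP 10.2 speaks of all disease-related complications and states no causality exclusion. If an attributed bleed is entered in both records, the complications table is complete and, apart from the Day 1 rule, fair. This stands as a limit on the claim. The protocol wording points to one record or the other, but the CRF is not available to settle it.

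A reader might also infer that every ACLF complication is affected. The documents do not support that:

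- **Organ failure:** the row in SAP 10.2 uses the CLIF-C OF sub-scores of SAP 9.3.8. These do not depend on causality, and 9.3.8 compares the arms.
- **SBP:** it is counted in the pooled infection analyses.
- **HE and ascites:** HE severity is partly covered by the brain and Child-Pugh encephalopathy sub-scores (SAP 9.3.2, 9.3.5). Ascites is partly covered by its Child-Pugh sub-score and grade (9.3.5, 9.3.13).

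Nor does attribution alone decide what becomes an AE. Deterioration that is not anticipated is an AE in either arm (8.3.3.1). Section 5.3.2 lists severe bleeding, GI or other, as an adverse event with no causality condition. Section 8.3.1 requires expected procedural events to be reported. Only GI bleeding is named as progression, and the documents do not say how other bleeding is classed. These points narrow the claim, but 5.3.2 and 8.3.10 also give different answers for a severe GI bleed, so the routing is less predictable.

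Finally, both records are tabulated and listed by arm, and laboratory values and blood-product use are summarised as well. The bleeding question is therefore not unanswerable. The planned summaries simply do not answer it directly.

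**Conclusion.** The point holds for GI bleeding and HRS, and in part for HE episodes. The stated rule allows a difference between arms in where an event is recorded, and no planned table removes it. Under the assumed ranges the complications table can show a risk ratio of 0.90 to 0.50 when there is no true difference, while the AE table shows 1% to 15% against 0%. These figures rest on assumed values of r and f and on an attributed event being recorded only as an AE. At f = 0 the distortion is nil. The documents therefore do not support saying that the tables will mislead, only that they can.

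The Day 1 gap follows from the text alone and needs none of these assumptions. The survival endpoints do not depend on this routing. The change should be made because it concerns an expected risk of the procedure and costs little.

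**What to change.** Add to SAP 10.2 one table by arm with rows for GI bleeding, all bleeding, HRS and HE. Count each subject once per row if the event is in either the AE or the complications record, from randomization (including Day 1) to Day 90, regardless of attribution. Give a descriptive risk difference with 95% CI, based on the actual final number of subjects. Define the bleeding rows by a term list fixed in advance. Counting each subject once makes the table right whether or not the two records overlap, and it follows what SAP 9.3.9 and 9.3.10 already do for infections.

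State how events on Day 1 itself are counted in SAP 10.2. Reconcile Protocol 5.3.2 with 8.3.3.1 and 8.3.10 on how severe bleeding is recorded, and state in the clinical study report which rule sites followed.

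The cost is a paragraph of SAP text and one table from data already collected. The primary analysis does not change. If the safety tables have already been run, the table can be reported as an additional analysis, which SAP Section 2 allows.

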8.3.11 Reporting of Serious Adverse Events

8.3.11.1 Reporting of Serious Adverse Events

Any SAE (see [Section 8.3.7](#)) that occurs after **signing the study ICF through the Final Visit (ie, end of study [Day 90 visit] or early discontinuation visit)** must be expeditiously reported whether or not considered attributable to the study drug. Each SAE must be fully recorded in the subject’s eCRF and SAE Report Form. In addition, any SAE that occurs after the end of the study (Day 90) should be reported if the investigator feels that the event is related to the use of IP.

SAEs will be reported using the designated SAE Report Form. When the investigator becomes aware of an SAE, she/he must submit a completed, signed and dated SAE Report Form (in English) **within 24 hours** to the Sponsor by email/fax. The date of this SAE discovery by the study center should be documented in the source documents (ie, medical records).

Each SAE must be followed up until resolution or stabilization. After the initial report, all relevant information for SAE follow-up, and for the outcome, must also be supplied to the Sponsor in a timely manner (within 3 days from its identification or within 24 hours for relevant new information) by means of the SAE Report Form. In addition, the Sponsor or contract research organization may request additional information and/or reports.

All SAE Report Forms must be reported to:

Grifols Global Pharmacovigilance

Email: [REDACTED]

FAX (back-up only): [REDACTED] (International)

GRIFOLS
 
Bioscience Industrial Group
	Number	BIG-CL-PRT-000002	Version	6.0	Status	Retired	Effective Date	29-Mar-2023
	IG1407 - Effects of Plasma Exchange with Human Serum Albumin 5% (PE-A 5%) on Short-term Survival in Subjects with "Acute-On-Chronic Liver Failure" (ACLF) at High Risk of Hospital Mortality						Page	73 of 102

When required, and according to local law and regulations, SAEs must be reported to the IRB/EC and regulatory authorities. Copies of the investigator's reports must be sent to the sponsor.

